11.7 Interim Analyses

No interim analysis is planned.

11.8 Determination of Sample Size

One hundred patients will be randomized for the DB1 treatment period. Patients who discontinue participation without completing the study protocol will not be replaced.

The primary endpoint is the comparison of the proportion of patients who are pain-free at 2 hours after the first dose of study medication. It is assumed that 15% of placebo and 42% of DFN-02 (treated) patients will be pain-free at 2 hours. A sample size of 50 patients in each DB1 dosing arm will provide 81% power to detect this assumed difference between placebo and DFN-02 at a 5% (2-sided) level of significance.

12 Quality Assurance and Quality Control

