6.1 Overall Study Design and Plan

This is a randomized, 2 DB treatment period dosing study, to be conducted at multiple centers in the US. Previously diagnosed patients with a history of episodic migraine (as defined by International Classification of Headache Disorders, 3rd edition [beta version]¹ [ICHD-3]), who experience an average of 2 to 8 migraine attacks per month for at least the past 12 months, with no more than 14 headache days per month, and with 48 hours of headache-free time between migraine, will be randomized in a 1:1 ratio in both DB periods to receive either DFN-02 (sumatriptan nasal spray) 10 mg or a matching placebo.

There will be a screening period to evaluate whether the patient fits the migraine inclusion criteria pursuant to ICHD-3, and does not have medication overuse. Patients with at least a 12-month medical history of acute migraine will be eligible for enrollment in the treatment period. Patients will continue to take their normal migraine medication during this screening period.

During the screening period, the electronic diary (eDiary) will be dispensed in order for the patient to enter information for daily check-in, record at least 1 migraine attack, and rescue medication use, to determine the patient's ability to properly use the eDiary. If eligible and randomized, patients in the DB1 treatment period will be instructed to use the study medication in 1 migraine attack as soon as (and no more than within 1 hour after) experiencing moderate to severe migraine pain (defined as headache pain rating of Grade 2 [moderate] or Grade 3 [severe] on a pain severity scale of 0 to 3). If the patient is not able to use study medication for the first migraine after randomization, they should be instructed to use the study medication for the next attack. Those patients who do not experience a migraine attack, and/or who do not treat any migraine attack with study medication or record eDiary data, will not be allowed to continue into the DB2 treatment period, and will be discontinued. After treating a migraine attack with study medication, patients should be instructed to contact the site within 24 hours of the treated migraine (or the next working day) to schedule their next visit.

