3.6. DETERMINATION OF SAMPLE SIZE

Approximately 100 subjects will be randomized for the DB1 treatment period. Subjects who discontinue participation without completing the study protocol will not be replaced.

The primary endpoint is the comparison of the proportion of subjects who are pain-free at 2 hours after the first dose of study medication. It is assumed that 15% of placebo and 42% of DFN-02 10 mg (treated) subjects will be pain-free at 2 hours. A sample size of 50 subjects in each DB1 dosing arm will provide 86% power to detect this assumed difference between placebo and DFN-02 10 mg at a 5% (2-sided) level of significance.

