8. EFFICACY

8.1. PRIMARY EFFICACY ENDPOINT AND ANALYSIS

8.1.1. Primary Analysis of the Primary Endpoint

The primary efficacy endpoint is the proportion of subjects who are free from headache pain at 2 hours after the first dose of study medication taken for a migraine attack with moderate to severe headache pain during the DB1 treatment period (ie, headache pain rating of moderate [Grade 2] or severe [Grade 3] predose reduced to none [Grade 0] at 2 hours postdose). The primary efficacy endpoint will be analyzed using Fisher's exact test.

Proportions of subjects free from headache pain at 2 hours postdose will be calculated as the number of subjects who are pain-free at 2 hours postdose divided by the number of subjects with non-missing assessment at 2 hours postdose. Missing primary efficacy endpoint data will be imputed using the last observation carried forward (LOCF). Results based on the LOCF data and the observed data will be displayed separately.

The number of subjects with response, the number of subjects with non-missing assessment, proportions for the DFN-02 10 mg and placebo groups, 95% exact CIs for those proportions, the odds ratio for response, and the corresponding p-value will be presented for the comparison between two treatment groups for the FAS1. This analysis will exclude subjects who took a second dose of study medication or rescue medication prior to the data collection of the 2 hours postdose time point (inclusive). The analysis will also be performed using the PPS.

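### The stated power is for 50 analysed subjects per arm, but only 50 per arm are randomized and no loss is allowed for; average Fisher power is about 79% at 10% loss and 74% at 20%

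*Protocol*

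**What the plan says.** **Size and power.** Protocol 11.8 fixes the number randomized and rules out replacement: "One hundred patients will be randomized for the DB1 treatment period. Patients who discontinue participation without completing the study protocol will not be replaced". The rates are given next: "It is assumed that 15% of placebo and 42% of DFN-02 (treated) patients will be pain-free at 2 hours". Then comes the power: "A sample size of 50 patients in each DB1 dosing arm will provide 81% power", tested "at a 5% (2-sided) level of significance". SAP 3.6 uses the same rates, arm size and alpha but reports a different figure: "A sample size of 50 subjects in each DB1 dosing arm will provide 86% power". It randomizes approximately 100 and repeats that "Subjects who discontinue participation without completing the study protocol will not be replaced". Allocation is 1:1 (protocol 9.1). Neither section gives an expected loss or an inflation of the 50.

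**Who leaves the primary analysis.** Three rules apply between randomization and the LOCF analysis:
- No treated attack. Protocol 6.1 foresees this: "Those patients who do not experience a migraine attack, and/or who do not treat any migraine attack with study medication" are discontinued. SAP 3.8 says the same, and FAS1 (SAP 5.4) requires a dose in DB1.
- No post-baseline efficacy rating in DB1 (SAP 5.4).
- Early second dose or rescue. SAP 8.1.1: "This analysis will exclude subjects who took a second dose of study medication or rescue medication prior to the data collection" at 2 hours, inclusive. The protocol builds the same exclusion into its FAS definition (11.2).

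SAP 8.1.1 also presents an observed-data version, whose denominator is subjects with a 2-hour rating. The planned test is Fisher's exact test (protocol 11.6.1, SAP 8.1.1).

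**The concern.** The calculation treats every randomized patient as analysed. Patients are randomized at Visit 2 and then have up to 4 weeks to meet and treat a moderate or severe attack, so some will probably not reach the analysis, and the plan has rules for them. Any such loss comes straight off the 50 per arm, and the protocol's 81% leaves only about one point above 80%.

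This is separate from the disagreement between 81% and 86%. Harmonising those two numbers would still leave a figure that assumes no loss. What is at stake is interpretation: a non-significant result would be read against a power that applies only if nearly every randomized patient is analysed.

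**Working it through.** **Inputs.** Placebo 15%, DFN-02 42%, 50 per arm, two-sided 5% (protocol 11.8, SAP 3.6); Fisher's exact test (protocol 11.6.1, SAP 8.1.1). Loss rates are assumptions, shown as a range.

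**Step 1: reproduce the stated figures at 50 per arm.**

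Exact power of Fisher's test is the sum, over all pairs of responder counts (x, y) with two-sided Fisher p ≤ 0.05, of Bin(x; n₁, 0.15) × Bin(y; n₂, 0.42). At 50/50 this gives 81.7%, in line with the protocol's 81%.

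The SAP's 86% comes from an uncorrected pooled z-test, with mean rate (0.15 + 0.42)/2 = 0.285:
- null SE = √(2 × 0.285 × 0.715 / 50) = 0.0903
- alternative SE = √((0.15 × 0.85 + 0.42 × 0.58) / 50) = 0.0862
- power = Φ((0.27 − 1.96 × 0.0903) / 0.0862) = Φ(1.08) = 86.0%

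So 81% matches the planned test and 86% does not. Both use 50 analysed per arm.

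**Step 2: randomized against powered.** 100 randomized 1:1 gives 50 per arm, the same 50 that enters the calculation. The implied loss is 50 − 50 = 0.

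**Step 3: Fisher power with fewer analysed, equal arms.**
- 50/50: 81.7%
- 49/49: 80.7%
- 48/48: 79.5%
- 45/45: 76.2%
- 40/40: 70.7%

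**Step 4: check whether equal arms are representative.** Fisher's test is discrete, so power does not move smoothly with arm sizes. With 96 analysed (placebo/DFN-02):
- 46/50: 82.0%
- 47/49: 83.0%
- 48/48: 79.5%
- 49/47: 82.5%
- 50/46: 82.3%

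The equal split is the low point here, so the Step 3 figures overstate the expected drop.

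**Step 5: average over random loss.** Let each of the 50 randomized per arm be lost independently with probability d, and weight the exact power of each resulting pair (n₁, n₂) by its binomial probability:
- d = 5%: 81.4%
- d = 8%: 80.1%
- d = 10%: 79.1%
- d = 15%: 76.5%
- d = 20%: 73.7% (73.6% if improbable arm sizes are not trimmed)

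The average passes below 80% a little above 8% loss.

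**The case against.** The other side has real force, and it limits how far the point goes.

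- **Losing two per arm.** A reader might infer from Step 3 that losing two per arm already takes the test below 80%. That is true only of an exact 48/48 split, by half a point; the other four splits shown for the same four losses give 82.0% to 83.0%. The documents also never name 80% as a design target. It serves here only as a reference line.
- **71 to 76% at 10 to 20% loss.** A reader might also infer this range from the equal-arm figures at 45 and 40. Those are low points; the averages are about 79% and 74%.
- **A power the design cannot reach.** This is too strong. With 5% loss the average is still 81.4%, and SAP 3.6 and protocol 7.1 randomize approximately 100, so slightly more could enter. That latitude is not a stated allowance for loss, however.
- **Missing 2-hour ratings.** These do not remove a subject from the LOCF analysis, only from the observed-data table.
- **Features that limit loss.** Entry requires an average of 2 to 8 attacks a month, a later attack may be treated if the first is missed, sites are advised to contact patients who report no attack for 2 to 3 weeks, and second dose or rescue is to follow the 2-hour entry. Loss may therefore be modest, but the documents do not say how much was expected.
- **Non-replacement.** Not replacing randomized patients is ordinary practice and not itself a fault.

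The SAP's 86% does not rescue the plan. On the pooled z-test 43 per arm would still give 80.3%, but that is not the planned test.

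What survives is narrower: power is stated for the number randomized, the analysis uses a subset, and the difference is not quantified.

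**Conclusion.** The point holds in its limited form. The stated power applies only with little or no loss. For the planned test it is 81.7% at 50 analysed per arm, and on average about 81%, 79%, 76% and 74% at 5%, 10%, 15% and 20% loss, passing below 80% at roughly 8 to 10%.

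This rests on three assumptions: the loss rates, which are not in the documents; loss that is independent between subjects and equally likely in both arms; and response rates of 15% and 42% among those analysed. The last need not hold if subjects excluded for early rescue differ in outcome from the rest. The shortfall is a few points at moderate loss. It calls for an honest restatement, not a redesign.

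**What to change.** In protocol 11.8 and SAP 3.6:
- say that the power refers to subjects analysed under SAP 8.1.1 with the two-sided Fisher's exact test;
- give the loss the sponsor expects between randomization and that analysis;
- restate the power at the resulting evaluable number, using averages over random loss (about 82% with no loss, 79% at 10%, 74% at 20%) and not the equal-arm low points.

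Make this in the same edit that reconciles 81% with 86%, since both touch the same sentence. The cost is one or two sentences per document and a less favourable stated figure. No extra enrolment is needed and no analysis rule changes.

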12.1.1 Audit and Inspection

The study site and study documentation may be subject to quality assurance audit during the course of the study by the Sponsor, INC Research, or its nominated representative. In addition, inspections may be conducted by regulatory authorities at their discretion.

CONFIDENTIAL

12.1.2 Monitoring

Source documents for this study include the eDiary and study files stored at the site. Electronic CRF data collection must be completed for each patient who signs an ICF.

In accordance with cGCP and International Conference on Harmonisation (ICH) guidelines, the study monitor will carry out source document verification at regular intervals to ensure that the data collected in the eCRF are accurate and reliable. The frequency of monitoring visits will be determined by the rate of patient recruitment.

The following will be reviewed, at a minimum, at these visits:

- Compliance with the protocol
- Consent procedure
- Source documents
- AE procedures
- Storage and accountability of study medication materials

The monitoring visits also provide the Sponsor with the opportunity to ensure the Investigator's obligations and all applicable ICH or health authority regulation requirements are being fulfilled.

The Investigator must permit the Medical Monitor, the IRB, the Sponsor's internal auditors, and representatives from regulatory authorities direct access to all study-related documents and pertinent hospital or medical records for confirmation of data contained within the eCRFs. All efforts to protect patient confidentiality will be upheld.

An electronic medical record may be the source document; however, the study site must provide a SOP that demonstrates the electronic medical record system is compliant with applicable regulations and details the review and approval of data entries by the principal Investigator.

Protocol deviations identified by the site or the study monitor should be reported to the IRB according to the IRB's reporting guidelines. All deviations will be recorded in the INC Research clinical trial management system and will be categorized as major or minor prior to data analysis.

12.1.3 Data Management and Coding

INC Research will be responsible for activities associated with the data management of this study. This will include setting up a relevant database (Medidata RAVE) and data transfer mechanisms, along with appropriate validation of data and resolution of queries. Data generated within this clinical study will be handled according to the relevant SOPs of the data management and biostatistics departments of INC Research.

Study site staff will enter data directly into the electronic data capture (EDC) system by completing the eCRF via a secure internet connection. Data entered into the eCRF must be verifiable against source documents at the study site. Any changes to the data entered into the EDC system will be recorded in the EDC audit trail, which is compliant with FDA Code of Federal Regulations 21 Part 11.

Data entered into the eCRF will be validated as defined in the data validation plan. External data checks will be programmed where appropriate (e.g., for laboratory data,

CONFIDENTIAL

ECGs) as well as for cross table checking between eCRFs (e.g., AE and concomitant medication forms).

Medical coding will use MedDRA version 19.0 or higher for concomitant diseases and AEs, and WHO-DD version March 2016 or later for medications.

Missing or inconsistent data will be queried electronically in the EDC system to the Investigator for clarification. Subsequent modifications to the database will be documented.

13 Records and Supplies

13.1 Drug Accountability

Upon receipt of the study medication, the Investigator (or designee) will conduct an inventory of the supplies and verify that study medication supplies are received intact and in the correct amounts before completing a supplies receipt. The Investigator will retain a copy of this receipt at the study site and provide the original receipt to the study monitor, to be stored in the trial master file. The inventory of supplies at the study site may be checked at any time during the study by the monitor.

It is the responsibility of the Investigator (or designee) to ensure that the study medication has been correctly documented for the amount received, dispensed, and returned on the dispensing log that will be provided. A full drug accountability log, provided by INC Research, will be maintained at the study site at all times. The study monitor will arrange regular collection of used and unused study medication returned by the patient. The study monitor will also perform an inventory of study medication at the close-out visit to the study site. All discrepancies must be accounted for and documented.

13.2 Financing and Insurance

Financing and insurance of this study will be outlined in a separate agreement.

14 Ethics

14.1 Institutional Review Board

Before initiation of the study at the study site, the protocol, all protocol amendments, the ICF, screenshots of eDiary assessments, and any other relevant study documentation will be submitted to the IRB. Written approval of the study and all relevant study information must be obtained before the study site can be initiated or the study medication released to the Investigator. Any necessary extensions or renewals of IRB approval must be obtained, in particular, for changes to the study such as modification of the protocol, the ICF, the written information provided to patients and/or other procedures. INC Research will submit relevant study documentation to the central IRB on behalf of the study sites.

In the event that a study site uses a local IRB, it is the responsibility of the site Investigator to obtain written approval of the study and all relevant study information prior to the initiation of study activities. Extensions or renewals of local IRB approval or approvals of changes to the ICF or other written information provided to patients will be the responsibility of the site Investigator.

CONFIDENTIAL

The Investigator will report promptly to the IRB any new information that may adversely affect the safety of the patients or the conduct of the study. INC Research will submit written summaries of the study status to the IRB annually or more frequently if requested by the IRB. On completion of the study, the Sponsor (or designee) will notify the IRB that the study has ended.

14.2 Ethical Conduct of the Study

This study will be conducted according to the Guidelines of the World Medical Association Declaration of Helsinki in its revised edition (Brazil, 2013) and the ICH guidelines for cGCP as well as the demands of national drug and data protection laws and other applicable regulatory requirements.²⁹⁻³¹

14.3 Patient Information and Consent

The Investigator is responsible for ensuring that no patient undergoes any study-related examination or activity before that patient has given written informed consent to participate in the study. The written consent must be given by the patient after detailed information about the study has been given and in accordance with any national provisions on the protection of clinical study patients. The verbal explanation will cover all the elements specified in the written information provided for the patient.

The Investigator or sub-Investigator will inform the patient of the objectives, methods, anticipated benefits, and potential risks and inconveniences of the study. The patient should be given every opportunity to ask for clarification of any points he or she does not understand and, if necessary, ask for more information. At the end of the interview, the patient will be given time to consider the study, if this is required, or if the patient requests more time. Patients will be required to sign and date the ICF. Patients should be able to read and write; the use of a legally authorized representative is prohibited in this study. After signatures are obtained, the ICF will be kept and archived by the Investigator in the Investigator's study file for possible inspection by regulatory authorities, the IRB, [name], INC Research personnel, or third parties authorized by [name]. Patients will be given a signed copy of the ICF for their records.

It should be emphasized to the patient that he or she is at liberty to withdraw from the study at any time, without penalty or loss of benefits to which the patient is otherwise entitled. Patients who refuse to give or who withdraw written informed consent should not be included or continue in the study.

14.4 Patient Confidentiality

All personal data collected and processed for the purposes of this study should be managed by the Investigator and his/her staff with adequate precautions to ensure confidentiality of those data, and in accordance with the American Health Insurance Portability and Accountability Act of 1996 (HIPAA)³² and applicable local laws and/or regulations on personal data protection.

Monitors, auditors, and other authorized agents of the Sponsor or INC Research, the IRB approving this research as well as that of any applicable regulatory agency, will be granted direct access to the study patients' original medical records for verification of clinical study procedures and/or data, without violating the confidentiality of the patients to the extent permitted by the law and regulations. In any presentations of the results of this study, or in publications, the patients' identity will remain confidential.

CONFIDENTIAL

15 Reporting and Publication, Including Archiving

Essential documents are those documents that individually and collectively permit evaluation of the study and quality of the data produced. After completion of the study, all documents and data relating to the study will be kept in an orderly manner by the Investigator in a secure study file. This file will be available for inspection by the Sponsor or its representatives. Essential documents should be retained for 2 years after the final marketing approval in an ICH region or for at least 2 years since the discontinuation of clinical development of the study medication. It is the responsibility of the Sponsor to inform the study site of when these documents no longer need to be retained. The Investigator must contact the Sponsor before destroying any study-related documentation. In addition, all patient medical records and other source documentation will be kept for the maximum time permitted by the hospital, institution, medical practice, or federal law. The Investigator shall not publish any articles or make any presentations relating to the study medication or referring to data or materials generated as part of the services provided under this agreement, without the prior written consent from the Sponsor; such consent shall not be unreasonably withheld.

1. GLOSSARY OF ABBREVIATIONS

Abbreviation	Description
ADD	Attention Deficit Disorder
ADHD	Attention Deficit Hyperactivity Disorder
AE	Adverse Event
ALT	Alanine Aminotransferase
AST	Aspartate Aminotransferase
ATC	Anatomical Therapeutic Chemical
BMI	Body Mass Index
CAD	Coronary Artery Disease
CI	Confidence Interval
CRF	Case Report Form
DB	Double-Blind
DBP	Diastolic Blood Pressure
ECG	Electrocardiogram
eDiary	Electronic Diary
FAS	Full Analysis Set
HbA1c	Glycosylated Hemoglobin
HBsAg	Hepatitis B Surface Antigen
HCG	Human Chorionic Gonadotropin
HCV	Hepatitis C Virus
HIV	Human Immunodeficiency Virus
ICH	International Conference on Harmonization
ICHD-3	International Classification of Headache Disorders, 3rd Edition (Beta Version)
ID	Identification
IWRS	Interactive Web Response System
LOCF	Last Observation Carried Forward
MAO-A	Monoamine Oxidase-A
MBS	Most Bothersome Symptom

Statistical Analysis Plan

Final V1.0

[name], Ltd.
Protocol #DFN-02-CD-012
INC Research #1007752

Abbreviation	Description
MedDRA	Medical Dictionary for Regulatory Activities
MOH	Medication Overuse Headaches
N/A	Not Applicable
PPMQ-R	Patient Perception of Migraine Questionnaire-Revised
PPS	Per Protocol Set
PT	Preferred Term
QC	Quality Control
SAE	Serious Adverse Event
SAP	Statistical Analysis Plan
SAS®	Statistical Analysis System
SBP	Systolic Blood Pressure
SI	Standard International System of Units
SNRI	Serotonin Norepinephrine Reuptake Inhibitor
SOC	System Organ Class
SOP	Standard Operating Procedure
SS	Safety Set
SSRI	Selective Serotonin Reuptake Inhibitor
TEAE	Treatment Emergent Adverse Event
TLF	Table, Listing and Figure
TSH	Thyroid-Stimulating Hormone
ULN	Upper Limit of Normal
WHO	World Health Organization
WHO-DD	World Health Organization Drug Dictionary

Statistical Analysis Plan

Final V1.0

[name], Ltd.
Protocol #DFN-02-CD-012
INC Research #1007752

